**Reject (NC in subsequent LA epidural infusion)**

1. Pain >2 at 30 mins s/p initial LA load of 15 ml 0.125% bupivacaine with 10 mcg of sufentanil, without a bilateral T10 sensory level
2. Top-up (5-15ml 0.25% bupivacaine epidurally for all instances of request of additional analgesia) c/out pain >1 c/in 30 mins (i.e. catheter malfunction)
3. Progression to cervical dilatation >8 cm c/or delivers in 2 hrs from epidural placement (i.e. precipitous labor)
4. Progression to CS before 8 cm cervical dilatation
5. Patient request
6. Managing clinician's request
7. Changes to the maintenance regimen

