**Experimental design**

Pregnant women who present to Labor and Delivery for an anticipated vaginal delivery will be identified as potential participants based on inclusion/exclusion criteria and their desire for labor epidural analgesia. Once identified, interested candidates will be fully informed of the study procedures, have all

questions answered, and informed consent obtained. Pregnant participants will receive a labor epidural upon the patient's request and the epidural catheter will be initiated with 15 ml 0.125% bupivacaine with 10 mcg of sufentanil (our current standard of care loading dose).

Patients will be randomized into 1 of 4 group. Either group I or II in Study Part A and group III or IV in Study Part B in a double-blinded design. Each study part will run in parallel and independently. We have separated the study into 2 parts to clarify the methodology and aims for purposes of IRB and study design protocols.

*Study Part A:*

Group 1 Starting Concentration CEI: Bupivacaine 0.06% at 10 ml/hour + Sufentanil 5 mcg (2 ml) /hour (start at 0 mins)

Group 2 Starting Concentration PIEB: Bupivacaine 0.06% 10 ml q 60 + Sufentanil 5 mcg (2 ml) q60 (start at 30 mins)

Top-Up: 5-15ml 0.25% bupivacaine for all instances of request of additional analgesia (a current standard of care treatment option for breakthrough pain)

Bupivacaine 0.06% mg/ml in 250 ml NS bag and sufentanil 2.5 mcg/ml in 100 ml NS bag.

\*Top-up is an additional dose provided upon patient request in the setting of inadequate analgesia during labor. Bupivacaine concentration to increase or decrease by 0.01% in subsequent patient depending on success or failure of previous patient

*Study Part B:*

Group 3: CEI Bupivacaine 0.06% 10 ml/hour + PIEB Sufentanil 5 mcg (2 ml) bolus q60 mins

Group 4: PIEB: Bupivacaine 0.06% 10 ml q 60 mins + CEI Sufentanil 5 mcg (2 ml)/hr continuous infusion 0.5 mcg/ml

PIEB start at 30 mins and CEI start at 0 mins.

Top-Up: 5-15ml 0.25% bupivacaine for all instances of request of additional analgesia (a current standard of care treatment option for breakthrough pain)

Bupivacaine 0.06% mg/ml in NS; 250 ml bag.

Sufentanil bag 2.5 mcg/ml in NS; 100 ml bag.

Bupivacaine concentration to increase or decrease by 0.01% in subsequent patient depending on success or failure of previous patient. Protocol success/failure/reject in each group (which will affect the subsequent patient's dose in the randomized group) will be determined by the following criteria:

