Success - No supplemental analgesia request until vaginal exam c/w 8 cm dilation or more -> 0.01% w/v reduction in subsequent participant's local anesthetic.

Failure - Supplemental analgesia request c vaginal exam c/w less than 8 cm dilatation ->0.01% w/v increase in subsequent LA infusion.

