## 8. Other

\*No study number assigned to patients who meet protocol 'reject' criteria. Upon reject, catheter management at discretion of anesthesia care provider. No collection of subsequent data (secondary outcome measures).

In addition to demographic and obstetric data, data collection as described below.

Data Points:

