### iii. Verbal Pain Scores (0-10; average pain at peak of contractions; obtained by investigator):

1. Initial epidural request
2. 30 mins s/p epidural initial dosing (average peak of last contraction)
3. q 1 hour (average pain at peak of contractions)
4. At request for addl analgesia
  - a. 30 mins s/p top-up
5. At time of exam that establishes complete cervical dilatation (if known)
6. Average peak pain score during pushing (obtained c/in 1 hour post-partum)

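### Reject item 2 is worded as the reverse of its own gloss, and its implied priority over Failure should be made explicit

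*Combined protocol and SAP*

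**What the plan says.** The Experimental design section sorts each woman into one of three classes and uses the result to set the next concentration: "Protocol success/failure/reject in each group (which will affect the subsequent patient's dose in the randomized group" is the controlling phrase. The definitions are:

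- "Success - No supplemental analgesia request until vaginal exam c/w 8 cm dilation or more": the next woman's concentration goes down by 0.01%.
- "Failure - Supplemental analgesia request c vaginal exam c/w less than 8 cm dilatation": the next woman's concentration goes up by 0.01%.
- Reject: no change for the next woman. The note under 8. Other adds "No study number assigned to patients who meet protocol 'reject' criteria", and no later data are collected.

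Top-ups are tied to requests: "Top-Up: 5-15ml 0.25% bupivacaine for all instances of request of additional analgesia". Reject item 2 concerns a top-up "c/out pain >1 c/in 30 mins (i.e. catheter malfunction". Item 1 of the same list concerns the initial load and begins "Pain >2 at 30 mins s/p initial LA load". The Verbal Pain Scores list already includes a score at "30 mins s/p top-up". The primary outcome is the MLAC, estimated from the up-down sequences by the Dixon and Massey method.

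**The concern.** The three-way call produces the data for the primary analysis. It fixes the concentration the next woman receives and decides whether the present woman enters the sequence at all. A reject rule whose operative words contradict its own explanation could be applied in opposite ways by different staff.

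The item also overlaps with Failure by construction, because the event that triggers a top-up is the event that defines a Failure below 8 cm. If rejects removed mainly true Failures, upward steps would be lost and the sequence would drift below the median effective concentration. If they removed mainly Successes, it would drift above it.

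**Working it through.** **Text check.** Elsewhere in the protocol the shorthand *c* stands for with and *c/in* for within, so *c/out* reads as without. Item 2 is then met when pain does not exceed 1 after the top-up, which is relief. The gloss, catheter malfunction, means no relief. Item 1 agrees with the gloss: there, pain above a threshold marks an inadequate block.

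| Event below 8 cm, exam available | Failure? | Item 2, words | Item 2, gloss |
|---|---|---|---|
| Request, top-up works | yes | Reject | not Reject |
| Request, top-up does not work | yes | not Reject | Reject |

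Each column for item 2 contains one row that is both Failure and Reject. At 8 cm or more the same overlap exists between Success and item 2, because the item has no dilatation limit.

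**Size.** The plan gives no figure on this point to reproduce. The following are assumptions that are not in the documents: normal tolerance distribution, true MLAC 0.060%, SD 0.01-0.03%, and 80-95% of top-ups effective. From the documents: start 0.06%, step 0.01%. The sample size can be read as 80 or 40 per arm.

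Let f be the share of true Failures that are rejected, a the share of Successes rejected, and s the success probability where the sequence settles. Down-steps and up-steps balance when s(1−a) = (1−s)(1−f), so

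s = (1−f) / [(1−f) + (1−a)].

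- Gloss, Reject governs, a = 0: f = 0.05, 0.10, 0.20 gives s = 0.487, 0.474, 0.444.
- Words, below 8 cm only, a = 0: f = 0.80, 0.90, 0.95 gives s = 0.167, 0.091, 0.048, that is EC17 to EC5.
- Words, with half of Successes also topped up later: f = 0.80, a = 0.40 gives 0.20/0.80 = 0.25; f = 0.95, a = 0.475 gives 0.05/0.575 = 0.087.
- Words, only at 8 cm or later: f = 0, a = 0.40 gives 1/1.6 = 0.625, which is above the EC50. The shift is SD × 0.319, or +0.003% to +0.010%.

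Simulated Dixon-Massey MLAC, 80 counted per arm, floor at zero:

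| Handling | SD 0.01% | SD 0.02% | SD 0.03% |
|---|---|---|---|
| Gloss, 95% effective | 0.0597 | 0.0594 | 0.0590 |
| Gloss, 80% effective | 0.0588 | 0.0574 | 0.0561 |
| Words, 80% effective | 0.0509 | 0.0416 | 0.0326 |
| Words, 95% effective | 0.0440 | 0.0276 | 0.0151 |
| SE under gloss | 0.0016 | 0.0029 | 0.0043 |

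Results at 40 per arm are nearly the same, with SEs of 0.0022, 0.0040 and 0.0058. The gloss costs about 2-10 rejects per 80 counted. The words cost about 2-9 rejects per counted woman, or roughly 160-720 to count 80.

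**Order of Failure and Reject, gloss followed.** If malfunction itself causes 5% or 10% of women to request (assumed), Reject-governs gives 0.060%. Failure-governs gives 0.0610, 0.0614, 0.0622% (5%) and 0.0621, 0.0633, 0.0645% (10%) across the three SDs. The gap is 0.5-1.3 SE at 80 per arm; for example, (0.0621−0.0600)/0.0016 = 1.3. At 40 per arm it is 0.3-0.9 SE.

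**Between arms.** With true values 0.06% and 0.08% (assumed; difference 0.020%, ratio 1.33) and the same handling in both, the gloss gives a difference of 0.019-0.020% and a ratio of 1.32-1.34. The words applied below 8 cm give 0.016-0.020% and 1.39-2.09. Subtracting a similar amount from both arms leaves the difference roughly intact but inflates the ratio.

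**The case against.** The strongest reply is that the protocol can be used as it stands. Success, failure and reject are presented as a single call. The no-change instruction heads the whole Reject list, and a woman who meets a reject criterion gets no study number, so she is hard to count as a Failure. Item 3, on precipitous labor, points the same way: it would often describe a Success and would have little purpose unless Reject prevailed. The gloss then settles the intent, and staff who reject for catheter malfunction would not discard women whose top-up worked.

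Most of this stands. A reader might infer that the plan leaves Failure and Reject in open conflict. The documents do not support that: precedence for Reject is implied, though nowhere stated. A reader might also infer that the trial will estimate something near the EC5-EC17. That requires literal use throughout, and the number of rejects would be noticed. Nor does every partial literal use lower the MLAC, since use confined to top-ups at 8 cm or later raises it.

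Two things remain. The operative words still say the opposite of the gloss. And the gloss does not by itself restore a measurable criterion, because more than one rewording of the pain condition would agree with it.

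A further limit applies to the overlap. The Failure definition needs an exam, and dilatation at the time of a request is recorded only if known, so the overlap is certain only when an exam is available.

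**Conclusion.** The point holds as a wording error in an operative rule, together with a precedence that is implied but not written. With the gloss followed and Reject governing, the effect is small: 0.056-0.060% against an assumed 0.060%. Leaving the order unstated matters modestly at most.

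The large shifts are bounds that apply only if the words are used in full. How far any partial or mixed use would move the MLAC, and for mixed use in which direction, cannot be estimated from the documents. It would be wrong to conclude that the comparison between arms is immune: the absolute difference is largely preserved under equal handling, but the first aim is relative potency, and the ratio is distorted if the words are applied below 8 cm.

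All sizes rest on the assumed tolerance distribution, true MLAC, top-up effectiveness and malfunction rate. The text finding rests on none of these. Severity: a minor to should-fix wording correction.

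**What to change.** Reconcile the wording of item 2 with its gloss and with the Failure definition, so that each response to a top-up leads to one classification. The sponsor decides the clinical criterion. Add one sentence stating which call governs when a woman who is a Success or a Failure also meets a reject item, including when the top-up is given at 8 cm or later.

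The cost is a two-sentence protocol edit. The 30-minute post-top-up pain score that the rule needs is already collected, and no patients or procedures are added.

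### Reject rule 3 excludes fast labour only beyond 8 cm, while Success starts at 8 cm, so a woman at exactly 8 cm within 2 hours is scored Success and lowers the next concentration

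*Combined protocol and SAP*

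**What the plan says.** All four rules are in the protocol, in the Success/Failure definitions that close Experimental design and in the Reject list that follows.

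- Success: "No supplemental analgesia request until vaginal exam c/w 8 cm dilation or more". No minimum time since placement is given. The consequence is a "0.01% w/v reduction in subsequent participant's local anesthetic".
- Failure: "Supplemental analgesia request c vaginal exam c/w less than 8 cm dilatation", with a 0.01% increase for the next participant.
- Reject 3: "Progression to cervical dilatation >8 cm c/or delivers in 2 hrs from epidural placement", glossed there as precipitous labour.
- Reject 4: "Progression to CS before 8 cm cervical dilatation".

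The heading of the Reject list says that a reject leaves the next concentration unchanged. The note after the last list item (Other) adds that women who meet reject criteria get no study number and that no further data are collected from them.

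**The concern.** Success, Failure and Reject 4 meet at 8 cm without gap or overlap. Reject 3 alone uses a strict inequality, and no reason is given for the difference.

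Reject 3 appears to be there to remove women who reach the endpoint so soon that the result says little about the maintenance concentration. Every group receives the same loading dose, so the early outcome is the least informative about the assigned concentration. At exactly 8 cm that protection stops, although 8 cm is where the endpoint is reached.

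The trial admits multiparous women, and dilatation is recorded in centimetres, so 8 is an ordinary reading. Each such Success sends the next woman in that group one step down. Successes that owe more to fast labour than to concentration pull the sequence, and the group's MLAC, downward. MLAC is the primary outcome. The listed cervical-exam data points cover placement and requests for additional analgesia, not the first exam at 8 cm or more, so relabelling afterwards from the listed data may not be possible.

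**Working it through.** **Step 1: apply the rules.** Take a woman with no supplemental request, classified by the largest dilatation found within 2 hours and by whether she has delivered by then. Reject overrides Success, as the note after the Reject list implies.

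| Largest dilatation within 2 h | Delivered by 2 h | Success wording met | Reject 3 met | Effect on next concentration |
|---|---|---|---|---|
| 7 cm | no | not yet | no | not yet decided |
| 7 cm | yes | no | yes | none |
| 8 cm | no | yes | **no** | **-0.01%** |
| 8 cm | yes | yes | yes | none |
| 9 or 10 cm | no | yes | yes | none |
| 9 or 10 cm | yes | yes | yes | none |

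Exactly one cell is out of line: 8 cm, not delivered. With Reject 3 worded as 8 cm or more, that cell would become a Reject and no other row would change its Reject 3 status.

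**Step 2: illustrative size.** The plan states no figure for this, so there is none to reproduce. Inputs:

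- From the documents: step 0.01%, starting concentration 0.06%, and 80 women in a sequence (the stated 80 per study group).
- Assumed: the share *f* of scored women in the cell, and the SD of the concentration-response (tolerance) distribution. The documents give neither.

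For *f*, suppose 5% to 15% of women reach the endpoint within 2 hours and one third of first qualifying exams read exactly 8. Then *f* = 0.05 × 1/3 = 1.7% to 0.15 × 1/3 = 5%. I use 2% and 5%, with 10% as a stress value.

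If a share *f* succeeds whatever the concentration, the sequence settles where *f* + (1 − *f*)F(x) = 0.5, so F(x) = (0.5 − *f*)/(1 − *f*) and the shift is SD × z(F).

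- *f* = 2%: F = 0.48/0.98 = 0.4898, z = −0.0256. Shift −0.00026% w/v (SD 0.01%) or −0.00051% (SD 0.02%).
- *f* = 5%: F = 0.45/0.95 = 0.4737, z = −0.0660. Shift −0.00066% or −0.00132%.
- *f* = 10%: F = 0.40/0.90 = 0.4444, z = −0.1397. Shift −0.0014% or −0.0028%.

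Simulated Dixon-Massey estimates (80 women, 4,000 runs, true median 0.06%) moved slightly more:

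- *f* = 2%: −0.00036% (SD 0.01%) and −0.00077% (SD 0.02%).
- *f* = 5%: −0.00091% and −0.00165%.
- *f* = 10%: −0.0020% and −0.0034%.

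Taking both methods together, 2% to 5% gives about 0.0003% to 0.0017% w/v. The top of that range is 0.0017/0.01, about one sixth of a step. In the same simulations, with no such women, the sampling SD of one group's estimate was 0.0016% (SD 0.01%) and 0.0029% (SD 0.02%). The shift at 5% is therefore under 0.6 of that sampling SD (0.00165/0.00289 = 0.57; 0.00091/0.00157 = 0.58).

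**The case against.** **The boundary is a definition.** The plan defines precipitous labour as beyond 8 cm, or delivery, within 2 hours, so a woman at exactly 8 cm is not precipitous by its own terms. That is fair: the plan does not misclassify her against its own definition. What stands is that the other three rules meet at 8 cm, this one does not, and no reason is offered.

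**The cell is narrower than all first readings of 8 cm.** A woman at 8 cm at 60 minutes who passes 8 cm, or delivers, by 120 minutes is a Reject. One who asks for analgesia before 8 cm meets the Failure wording instead. Some of those left would have succeeded on the drug anyway. This stands, and it makes the shares above upper bounds under their own assumptions. Discretionary removal ("Managing clinician's request", or Other) is also possible, but neither is tied to 8 cm.

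**The bias is shared.** The same rule and loading dose apply in every group, so most of any shift should cancel in the comparison of PIEB with CEI. This stands too.

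**A stronger reading to avoid.** A reader might infer that the plan does not say which rule wins when two are met: for example 9 cm at 90 minutes with no request (Success and Reject 3), or a request at 5 cm followed by 9 cm before 2 hours (Failure and Reject 3). The documents do not support that. The note after the Reject list withholds a study number from anyone meeting reject criteria, and the list heading leaves the next concentration unchanged, so both women are rejects. Letting Success win would also leave the more-than-8-cm limb of Reject 3 without effect for any woman who made no request.

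**Conclusion.** The mismatch is real, and its consequence follows from the text: one case, exactly 8 cm within 2 hours with no request, no further progression and no delivery by 2 hours, is scored Success and lowers the next concentration by 0.01%, while 9 cm at the same time changes nothing.

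It is a minor point. With at most 2% to 5% of scored women in that case and a tolerance SD of 0.01% to 0.02%, all assumed, each group's MLAC falls by at most about 0.0003% to 0.0017% w/v. It bears on each group's absolute MLAC more than on the PIEB-CEI contrast. A reader might go further and infer that the between-group comparison is materially biased; nothing in the documents supports that. It is worth correcting because the label sets the next woman's concentration and the correction costs almost nothing.

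**What to change.** Reconcile the Success/Failure definitions with the Reject list so that outcome classification uses one 8 cm boundary in Success, Failure, Reject 3 and Reject 4. The investigators should confirm which cut point they intend. If Reject 3 is matched to the Success wording, the discordant cell closes and the other rules stay as they are. If the boundary is moved the other way, Failure and Reject 4 must be checked as well, so that exactly 8 cm still falls under a single rule. No extra sentence on precedence is needed.

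The cost is a very small text edit (a single inequality, if Reject 3 is the rule changed) and possibly a few more rejects to replace. It should be settled before the next outcome is scored, because each label feeds the following allocation.

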## 8. Other

\*No study number assigned to patients who meet protocol 'reject' criteria. Upon reject, catheter management at discretion of anesthesia care provider. No collection of subsequent data (secondary outcome measures).

In addition to demographic and obstetric data, data collection as described below.

Data Points:

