### iv. Additional Data Points

1. Overall Satisfaction c Labor Analgesia (0-100%; measured c/in 1 hr of delivery)
2. Labor Outcome: Spontaneous/Instrumented/Cesarean and total number of hours of oxytocin infusion prior to delivery
3. Neonatal Apgars (1 and 5 mins; assigned by pediatrician)
4. Pruritus q2 hrs (Y/N)
  - a. Requiring treatment
5. Nausea (0-10) Vomiting q2 hrs Y/N
  - a. Requiring treatment
6. Hypotension Requiring Treatment (Y/N)
7. Motor Weakness c Labor Analgesia (q2 hours; Straight leg raise Y/N)
8. Sensory level q2hrs
9. Duration of first and second stage of labor
10. Rupture of membranes (spontaneous or artificial) prior to epidural

*Inclusion criteria:* ASA I & II, Nulliparous and Multiparous, Spontaneous/Induced/Augmented Labor, Early active labor (cervix <5 cm (if known)), Pain (VPS) > 3, 18-45 years of age.

*Exclusion criteria:* <37 weeks gestation, H/o Cesarean Section, Multiple Gestation, Pre-eclampsia, Narcotics within 3 hours prior to labor epidural placement, Chronic Pain (as defined by chronic opiate consumption), Women who are participating in another study that will impact protocol

Our primary outcome or determinant of different treatments for labor pain is the minimal local anesthetic concentration of the final participants in each respective group upon study completion.

Interim analysis will be performed at 20 patients (10 in each group) in study part A and B, respectively. If

no important differences are detected, the study will end with the recruitment of 160 patients (80 for each study group) per our sample size calculation, based off an MLAC study by Ginosar, et al.

Demographic, obstetric and clinical outcome measures data will be analyzed using unpaired Student's, Mann-Whitney U-test, and Chi-Squared or Fisher's exact test as appropriate.

MLAC analysis: The median effective concentrations will be estimated from the up-down sequences using the method of Dixon and Massey (Dixon WJ, Massey FJ. Introduction to statistical analysis. 4th ed. New York: McGraw-Hill, 1983) that will enable MLAC with 95% confidence interval (CI) to be derived. The sequences will also be subjected to Wilcoxon and Litchfield probit regression analyses using  $\ln(1+x)$  transform as back-up or sensitivity tests.

*DATA SAFETY MONITORING PLAN* will follow standard of clinical care. Any adverse events will be reported to the PI and necessary adjustments to the protocol will be immediately instituted.

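### Rejected women get no study number and no further secondary data, so early cesareans drop out of the labor outcome by rule and safety is compared in women selected after randomization

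*Combined protocol and SAP*

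**What the plan says.** The reject list (section Reject) has seven named reasons and an open eighth, Other. Item 4 is "Progression to CS before 8 cm cervical dilatation", item 5 is the patient's own request, item 6 is "Managing clinician's request" and item 7 is "Changes to the maintenance regimen". Items 6 and 7 carry no limit on the reason. A reject leaves the concentration for the next woman unchanged.

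The note under 8. Other sets out what follows for the rejected woman: "No study number assigned to patients who meet protocol 'reject' criteria"; "Upon reject, catheter management at discretion of anesthesia care provider"; and "No collection of subsequent data (secondary outcome measures".

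Section iv. Additional Data Points lists the outcomes concerned. Item 2 is "Labor Outcome: Spontaneous/Instrumented/Cesarean and total number of hours of oxytocin infusion prior to delivery". Other items are Apgar scores at 1 and 5 minutes, pruritus, nausea and vomiting, treated hypotension and motor weakness. The same section plans between-group tests of obstetric and clinical outcomes. It defines no analysis set, no handling of missing data and no count of rejects by group. Its safety monitoring paragraph says "Any adverse events will be reported to the PI and necessary adjustments to the protocol will be immediately instituted".

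**The concern.** Leaving the next concentration unchanged after an uninformative case is a sensible rule for an up-down sequence. It gives no reason to stop following the woman for safety, yet the plan attaches both consequences to the same event.

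The reject event comes after allocation and may depend on treatment. A clinician who changes the infusion because of hypotension or leg weakness triggers item 6 or 7. A cesarean before 8 cm triggers item 4 and is itself one of the outcomes to be compared. The groups tested for safety are then no longer the randomized groups but those left after selection on later events. If selection differs between bolus and infusion, a difference in recorded rates may reflect rejection rather than the regimen. With no planned report of rejects by group, a reader could not judge this.

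**Working it through.** **No figure to reproduce.** The plan gives no reject rate, cesarean rate or adverse-event rate. Every rate below is an assumption chosen to show how the rule acts.

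**1. Which reject reasons can follow the start of study treatment?** Under Experimental design, continuous infusion starts at 0 minutes and programmed boluses at 30 minutes. Items 4, 5, 6 and 7 have no time limit and can occur at any later point. That is four of the seven named reasons. The plan does not say how often each occurs.

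**2. Cesarean: the loss follows from the rule itself.** Let c be the true cesarean rate and s the share of cesareans done before 8 cm. Ignoring other rejects, the retained women are a fraction 1 − cs of the total, and retained cesareans a fraction c(1 − s). The recorded rate is

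c(1 − s) / (1 − cs).

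| c | s | Calculation | Recorded rate |
|---|---|---|---|
| 20% | 50% | 0.100 / 0.900 | 11.1% |
| 15% | 25% | 0.1125 / 0.9625 | 11.7% |
| 15% | 50% | 0.075 / 0.925 | 8.1% |
| 15% | 75% | 0.0375 / 0.8875 | 4.2% |
| 30% | 70% | 0.090 / 0.790 | 11.4% |

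True rates of 20% and 30% can thus be recorded as almost the same figure (11.1% and 11.4%) if the timing of cesarean differs.

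**3. Apgar scores.** These are assigned after birth. For a woman rejected before delivery they are subsequent data, so they are not collected.

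**4. Other safety outcomes: the result depends on who is rejected.** Let p be the true event rate, a the probability of reject given the event and n the probability of reject without it. Suppose the rejected women are absent from the comparison. The recorded rate is

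p(1 − a) / [p(1 − a) + (1 − p)(1 − n)].

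Take hypotension at true rates of 20% and 10%:

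- *Same rejection in both arms, a = 50%, n = 10%.* 0.10 / (0.10 + 0.72) = 12.2% and 0.05 / (0.05 + 0.81) = 5.8%. Both rates fall and the 10-point difference shrinks to 6.4.
- *Rejection differs by arm, a = 50% against 10%, n = 10% in both.* 0.10 / 0.82 = 12.2% and 0.09 / (0.09 + 0.81) = 10.0%. The difference shrinks to 2.2 points.
- *Stronger imbalance, a = 75% against 25%, n = 0.* 0.05 / 0.85 = 5.9% and 0.075 / 0.975 = 7.7%. The order reverses.

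**5. Could another route restore the missing information?** Adverse events go to the principal investigator. The safety paragraph describes neither a comparison by group nor how a woman without a study number would enter one.

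**The case against.** The best defense is that the sole declared primary outcome is MLAC, that the aims concern potency and mechanism, and that no safety hypothesis is stated. The safety comparison would be weak anyway: with 80 per group and an assumed two-sided 5% level, power for 20% against 10% is about 42% even with no event-related rejection. This stands, and it limits the seriousness of the point. It does not justify selecting the women in whom safety is described.

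Several stronger readings are tempting, and the documents do not support them:

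- *The plan drops the women most likely to have been harmed.* This is an inference. Failed initial load, catheter malfunction and precipitous labor need not reflect harm from the regimen, and no reject frequencies are given. Only the loss of early cesareans is certain.
- *All recorded safety rates are too low.* This is certain only for cesareans lost through item 4. For the rest, direction depends on whether women with or without the event are rejected more often.
- *The event that triggers a reject is never recorded.* The note stops later data. Hypotension that leads to a regimen change comes before the reject and may be noted. What is missing is a stated route from that note into the analysis.
- *The number rejected cannot be recovered.* Consent and allocation records may exist, and staff must know of a reject to leave the next concentration unchanged. The supportable statement is that no report by group is planned.
- *The plan contradicts itself on cesarean or adverse events.* Cesareans at or after 8 cm remain recordable, so the outcome is truncated rather than contradicted. Adverse-event reporting makes no exception for rejected women, so it is not shown that the investigator would see an incomplete picture.

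**Conclusion.** The point holds for the secondary and safety outcomes and should be fixed. Followed exactly, the note removes every cesarean before 8 cm from the labor outcome and all Apgar scores of women rejected before delivery. The remaining safety outcomes are compared in groups selected after randomization. The size is unknown. Under the assumed rates, a cesarean rate of 15% to 30% is recorded as roughly 4% to 12%. A 20% against 10% hypotension contrast may shrink or, in one deliberately unequal scenario, reverse. The reversal shows what is possible and predicts nothing. The hypotension figures also assume that an event leading to reject stays out of the comparison, which the missing study number makes likely but the text does not say outright. The MLAC sequence and its rule for the next concentration are not in question.

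**What to change.** Replace the note under 8. Other with:

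> A study number is assigned at randomization. Reject leaves the next woman's concentration unchanged and removes the woman from the up-down MLAC sequence only. Mode of delivery, Apgar scores, hypotension requiring treatment, motor weakness, pruritus and nausea/vomiting continue to be recorded to delivery for all randomized women unless consent is withdrawn. They are compared by randomized group in all randomized women, with the time of reject recorded so that events before and after reject can be shown separately. The number and reasons of rejects are reported by group.

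The set should be all randomized women, not those who received study solution. Reject item 1 is judged at 30 minutes, when infusions have been running since 0 minutes but boluses are only due to start. In Part A, a treated set could therefore include such women in Group 1 and omit them in Group 2. Separating events before and after reject matters because later care is discretionary. That care stays as the protocol now states.

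The cost is one paragraph, slightly more data forms and continued two-hourly checks in rejected women. Mode of delivery and Apgar scores are ordinary delivery-record items. Safety rates may look less favorable. The MLAC analysis does not change.
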